This is a 24-week, two-arm, multicenter feasibility parallel randomized controlled trial designed to evaluate the usability and effectiveness of LuCApp to improve self-management of symptoms and quality of life in lung cancer patients. The protocol has been developed in accordance with the CONSORT-EHEALTH checklist (16). The flow diagram for recruitment and randomization is shown in Figure 1.

Figure 1 - Flow diagram for recruitment, randomization and data collection

Participants

Adults of both sexes with lung cancer (small and non-small cell) will be assessed for eligibility at participating sites. Study inclusion criteria will be (

Table 1):

- over 18 years of age individuals of both sexes;
- diagnosed with small or non-small cell lung cancer;
- patients eligible for chemotherapy, immunotherapy or biological therapy;
- patients diagnosed with non-resectable tumor and eligible for neoadjuvant therapies;
- life expectancy of six months or more;
- a performance status between 0 (asymptomatic) and 2 (symptomatic, <50% in bed during the day) according to the Eastern Cooperative Oncology Group (ECOG) score;
- patients fluently speaking Italian;
- patients able to provide informed consent to participate in the study;
- patients who own a smartphone that can access either the iOS or the Android platform.

Although internet literacy was not defined as an explicit eligibility criterion in this study, it works as a *de facto* selection criterion since only individuals that personally own a smartphone can be enrolled in the study. It was assumed that, if individuals owned a smartphone, they would be able to use it.

Patients will be excluded if they: i) are unable to provide written informed consent, ii) are unable to use the app and all other materials (i.e. blind), iii) have received, are receiving or plan to receive radiotherapy or surgical resection as their management will likely be different from patients undergoing pharmacological therapy. Furthermore, patients that are already included or about to join other clinical trials and individuals who are already using another smartphone application to self-manage cancer will not be considered eligible for the trial.

Table 1 - Summary of inclusion and exclusion criteria

Inclusion criteria	Exclusion criteria

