
• over 18 years of age individuals of both sexes;• diagnosed with small or non-small cell lung cancer;• patients eligible for chemotherapy, immunotherapy or biological therapy;• patients diagnosed with non-resectable tumor and eligible for neoadjuvant therapies;• life expectancy of six months or more;• a performance status between 0 (asymptomatic) and 2 (symptomatic, <50% in bed during the day) according to the Eastern Cooperative Oncology Group (ECOG) score;• patients fluently speaking Italian;• patients able to provide informed consent to participate in the study;• patients who own a smartphone that can access either the iOS or the Android platform.	
• individuals unable to provide written informed consent;• individuals unable to see the App and all other materials (i.e. are blind);• patients receiving or that plan to receive radiotherapy or surgical resection;• patients already included or about to join other clinical trials;• patients already using other smartphone applications to self-manage cancer symptoms.

Once eligibility has been established, patients will be asked to join the study by the medical oncologists after diagnosis and a face-to-face assessment at the participating centers. Patients will receive an invitation letter, the study leaflet and the informed consent form. This will not be a purely web-based trial, since face-to-face components will still be present: data will be collected through questionnaires via the app for the intervention patients, while standard-of-care patients will complete paper questionnaires during clinic visits, or at home (having received paper questionnaires during the previous visit) or via telephonic interviews with the research team. Outcomes will be self-assessed through Patient Reported Outcome Measures (PROMs) (for further information, please look at the “Outcomes” section) at different points in time. Patients assigned to the intervention arm will be trained to use LuCApp (study staff will provide them with a 15-minute presentation on how to use the App) and will be assisted during the whole study period by a “helpdesk”.

University and participating centers affiliations will be displayed on the invitation letter to obtain participants’ trust but no bias is expected to result from the display of such information.

Intervention (LuCApp)

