- 2) “Temperature” and “Weight” – Patients in the intervention arm will be asked to enter their body temperature everyday and to report their weight once per week (again via mobile banners or emails). Whenever body temperature exceeds the 38 degree Celsius threshold or a 5-percentage point reduction in body weight in the previous two weeks is reported, specific alerts will be generated to inform the clinical team in charge.
- 3) “Tip of the day” – Whenever a patient logs into the app, this feature of the app shows a daily tip, a short suggestion to better manage the side effects of the therapies. The tip is selected randomly among those related to the therapy the patient is undergoing. Tips were drawn from clinical practice guidelines and discussed by a consensus group of experts including medical oncologists, radiation oncologists, surgeons, nutritionists, speech language pathologists, infectious disease specialists, dentists and nurses (18, 19). All tips were later validated with the healthcare professionals from the three sites participating in the trial (final list is available as an attachment “4.1_LuCApp_Annex 1_Tips of the day”).
- 4) “Questionnaires” – A final section allows patients to fill-in several PROMs about their HRQoL and experience with supportive care needs and LuCApp: EuroQol 5D, Functional Assessment of Cancer Therapy (Lung), Hospital Anxiety and Depression scale, supportive care needs survey, usability and satisfaction with the app (see next section on outcomes). Data will be collected at several points in time, depending on the type of questionnaire considered (see next section on outcomes). Questionnaire completion is instrumental in evaluating several end-points and in determining whether LuCApp can improve patient-relevant outcomes compared to

the standard of care. To enable the comparison, patients in the standard of care arm will fill out the same questionnaires via paper at clinic visits or follow up.

[figure not shown]
- 5) “Trend” – In the Trend component, available in the healthcare professional App only, clinicians can access the longitudinal trend of their patients’ clinical parameters. Side effects, temperature and weight are displayed in charts, and it is possible to select a specific timeframe. Clinicians can access the same graphs remotely and analyze the progress of each patient’s clinical parameters and side effects over time (Figure 4).

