The ZBI was selected on the basis that it has been used in cancer patients (40) and is one of the most widely referenced scales in studies measuring caregiver burden (41). The ZBI was developed for nervous system disorders and mental disorders, but has also been applied to cancer patients (42-45). In one study, the authors explore if caregiver burden was in agreement with patient ratings. Patients had different forms of advanced cancer and their carer's Zarit scores were relatively low. They conclude that Zarit may not capture some important aspects of burden in cancer, given that it was initially developed for dementia patients (42). A second study used the ZBI to assess the impact of breathlessness in lung cancer patients on their caregivers, and found high levels of unmet needs and burden particularly in the more severe cases (43).

Assessment timing of the ZBI will be at the end of the study, and will be administered in paper format. Its criterion validity, construct validity and internal consistency have been demonstrated (40). The Italian version of the questionnaire is valid, reliable and useful for use in clinical contexts and in future studies (46).

(4) Usability and satisfaction of LuCApp

At the end of the study, patients in the intervention arm will have an opportunity to provide feedback on strengths and shortcomings of the application, including unintended/unexpected effects. This session will be of interest also for those who did not use the application as intended by the developers. Use and adoption metrics are important process outcomes to understand the mechanism of action of such intervention. The mHealth application contains a tracking system. Frequency and duration of logins and the activity will be recorded and evaluated. To test user satisfaction with the App, a modified computer system usability questionnaire (CSUQ) will be utilized at the end of the study and will be administered to both patients and clinicians using LuCApp. The CSUQ is an overall satisfaction questionnaire that was developed together with other subjective usability measures at IBM in the nineties (47). The CSUQ is identical to the Post-Study System Usability Questionnaire (PSSUQ),

[figure not shown]

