except that the wording of the items does not refer to a usability-testing situation but is rather appropriate for a field-testing situation. The CSUQ was later adapted for mobile apps usability testing to elicit participant satisfaction with the PAediatric Risk Assessment (PARA) app, a mHealth tool developed to help health care professionals in resource-limited settings detect patients at high risk of both in-hospital and post-discharge mortality (48). Based on this revised version, the questionnaire was further elaborated upon: the final version consists of 12 items evaluated on a Likert scale ranging from 1 (“Strongly agree”) to 7 (“Strongly Disagree”). In addition, three qualitative questions were added to draw further information on the application and on the generalizability of LuCApp in the current and other clinical contexts: 1) “What do you like the most about the App?”; 2) “What do you like the least about the App”; 3) “How could the App be changed to make it easier to use?”. No validated Italian version of the CSUQ was available, so the authors, in cooperation with healthcare professionals of the participating sites, developed the current version. The questionnaire will be administered at the end of the study.

(5) Resource use

The perspective taken for the evaluation of resource consumption will be that of the National Healthcare System. In order not to overload patients and the App design with additional modules, resource use will be captured through patients reports of symptoms and clinicians actions in response to those symptoms (e.g. prescriptions, hospitalization, change in therapy). Moreover, additional information will be obtained for both control and treatment group patients via a form administered by the physician during the clinics. Unitary costs will be expressed as euros 2018. Drug unitary costs will be derived from national price listings, laboratory and instrumental tests will be valued according to the outpatient procedures formulary in accordance with the ongoing policies of Lombardy Region as well as eventual hospitalizations.

Figure 6 summarizes the data collection process throughout the study.

Figure 6 - Time-points of outcomes assessment

Sample size

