The electronic and mobile health revolution holds great potentials for improving symptom management strategies in chronic conditions. With spending review reforms under way, using web- and mobile-based technology to develop low cost and pragmatic patient-centered intervention is the key to lessening the health care cost and advancing the science of symptom management. In parallel with the development of new strategies and products, the evaluation of such interventions becomes important in order to bring to patients and to healthcare systems effective and cost-effective solutions. This clinical trial focuses on primary outcomes of health related quality of life and usability to test preliminarily the impact of LuCApp as a technology to improve self-reporting and self-management of symptoms in patients with lung cancer. The trial was designed with a pragmatic “attitude”, eligibility criteria were intentionally set wide to capture the lung cancer population seen in real practice. However, this trial is to be intended as a pilot one in order to understand the usability and feasibility of introducing a new mobile technology in the management of symptoms and side effects of patients undergoing pharmaceutical treatments for lung cancer in three centers in Northern Italy.

Dissemination and impact

The protocol will be registered on a public repository and possibly published on a peer reviewed journal. Once the study will be completed and the analyses will be performed, a report will be produced and shared with all participating centers for interpretation. A manuscript will be drafted by the team and submitted for publication at conferences and in scientific journals.

REFERENCES

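### The usability questionnaire is given once, at the end of the study, and to patients only through the app, so its result may over-represent persistent users and lose the reasons for abandonment

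*Combined protocol and SAP*

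**What the plan says.** **Role of usability.** Under Trial design the protocol states: "This is a 24-week, two-arm, multicenter feasibility parallel randomized controlled trial", with usability named as an aim beside effectiveness. The Discussion adds: "This clinical trial focuses on primary outcomes of health related quality of life and usability".

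**Timing.** Outcomes, part (4), says that the modified usability questionnaire "CSUQ) will be utilized at the end of the study and will be administered to both patients and clinicians" who use LuCApp. The same part closes with "The questionnaire will be administered at the end of the study". The instrument has 12 items scored 1 (best) to 7 (worst). Three open questions ask what is liked most, what is liked least, and what would make the app easier to use.

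**Route.** The description of the intervention, component 4, places the questionnaire in a section of the app that "allows patients to fill-in several PROMs about their HRQoL and experience with supportive care needs and LuCApp". Its list ends with "usability and satisfaction with the app (see next section on outcomes". The Participants section says the same in general terms: "data will be collected through questionnaires via the app for the intervention patients". Completion on paper in clinic, on paper at home, or by telephone is described there and under Standard of care for control patients only.

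**Early exit.** Under Randomization, patients leave the study when cancer treatment stops, on withdrawal, when the study closes, or at death. No usability rating at exit is described.

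**Other sources.** Outcomes, part (4), also offers intervention patients a chance to give feedback at the end of the study, and remarks: "This session will be of interest also for those who did not use the application as intended by the developers". Login frequency, login duration and activity are recorded.

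**Analysis.** Statistical methods provides only a graphical and numerical summary of usability. It gives no denominator and no rule for patients without a rating.

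**The concern.** A patient who finds the app burdensome and stops opening it has, on the stated route, to reopen it in order to say so. A patient who has already left the study has no stated occasion to rate it. The ratings would then come mainly from people who were still in the study and still willing to use the app.

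Two things are at stake. The summary score may describe persistent users rather than everyone given the app. The open questions, which are the plan's main way to learn what should be changed, may also miss the patients with most to say. Both matter in a trial that presents itself as a pilot of usability and feasibility.

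**Working it through.** **Step 1. Who can be heard under the plan as written** (reading the end of the study as week 24):

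| Patient in the LuCApp arm | CSUQ and open questions | Feedback session | Login data |
|---|---|---|---|
| In study, using the app | Yes | Yes | Yes |
| In study, stopped using the app | Only if the app is reopened | In scope; mode and instrument not stated | Show that use stopped, not why |
| Left the study alive | None planned | None planned | Show use up to that point |
| Died before the end | None | None | Show use up to that point |

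**Step 2. The plan's own figures.** The documents give no sample size, precision target or success threshold for usability. The only loss figure is the 30% attrition under Sample size, attached to the 12-week TOI endpoint. For that endpoint (difference 6, SD 11.54, two-sided α 0.05, power 80%), the normal formula gives 2 × (1.960 + 0.842)² × 11.54² / 6² ≈ 58.1, so 59 per arm. The t-test calculation gives 60 per arm, or 120 in total with 80.6% power. The plan's 120 is reproduced, and its 156 equals 120 × 1.30.

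**Step 3. Patients without a rating.**
- LuCApp arm: 156 / 2 = 78.
- At 30% loss: 78 × 0.30 = 23.4, about 23 missing; 78 × 0.70 = 54.6, about 55 rated.
- If 60 are retained, as the target of 120 implies: 78 − 60 = 18 missing, and 18 / 78 = 23%.

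The two counts differ because 156 was obtained by multiplying by 1.30, not by dividing by 0.70. Both are shown as a range. Loss by week 24 could be larger, since the 30% refers to week 12. Patients who stay in the study but do not reopen the app would add to it.

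**Step 4. Can the missing-data plan fill the gap?** Carrying forward the last, minimum or average observation needs an earlier value, and an instrument given once has none. Multiple imputation is also listed, but it is not tied to usability. It would have to assume that leavers rate the app as similar stayers do, which is the point in doubt.

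**Step 5. Bounds for a proportion.** Let p be the share of responders who are satisfied and m the share missing. The share among all patients lies between p(1 − m), if no missing patient is satisfied, and p(1 − m) + m, if all are. The documents give no satisfaction rate and no cut-off for satisfied, so p = 0.80 is an assumption.
- m = 0.30: 0.80 × 0.70 = 0.56 to 0.56 + 0.30 = 0.86.
- m = 0.23: 0.80 × 0.77 = 0.62 to 0.62 + 0.23 = 0.85.

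At 30% missing, a reported 80% could be too high by up to 24 points or too low by up to 6.

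**Step 6. Shift in the mean score.** The responders' mean is too favourable by m × d, where d is how much worse the missing patients would have scored on the 1 to 7 scale. The documents do not give d. For d = 0, 0.5, 1 and 2 (assumed):
- m = 0.30: 0, 0.15, 0.30 and 0.60 points.
- m = 0.23: 0, 0.12, 0.23 and 0.46 points.

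**The case against.** A reader might infer that patients who abandon the app never rate it, and that the feasibility answer is therefore biased upwards. The documents do not support that much, for five reasons.

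- **Feedback session.** It expressly looks to patients who did not use the app as intended. Someone who stopped using the app but stayed in the study could be heard there, or could log in once to answer. This stands and rules out the word never. The session is still at the end of the study, though, and it has no stated mode, instrument or analysis.
- **Meaning of end of study.** The usability text does not say week 24. Since patients remain on study only until one of the listed exits, a patient-level end is possible, and living leavers could then be asked. The figure of assessment time points is not in the text available to this review and might settle it. Against this, the FACT-L schedule is given once as 12 weeks and the end of the study period, and once as 12 and 24 weeks, so week 24 is the more natural reading.
- **Breadth of feasibility.** Login data cover everyone given the app, and clinicians complete the CSUQ too. Abandonment itself would be seen. What would be missing is the patient's rating and reasons.
- **Direction.** Death or the end of cancer treatment need not reflect dislike of the app, and the bounds in Step 5 include no bias and downward bias. This stands.
- **Consequence.** The Sample size section defines the primary outcome as 12-week TOI change, and no test or go/no-go rule rests on usability. This limits the harm. It does not remove it, because the documents make usability a stated purpose of the trial.

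**Conclusion.** The concern holds as a limitation of the stated design. There is one end-of-study rating, the app is the only stated route for patients, and there is no exit rating and no rule for non-responders. The usability result may therefore over-represent persistent users, and the reasons for abandonment may go uncollected.

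Between 18 and 23 of 78 LuCApp patients would have no rating if the 12-week attrition allowance also held at the end of the study. An upward bias is likely, because burden is an obvious reason to stop. Its direction and size nevertheless depend on ratings that the documents do not supply, and the 56% to 86% range rests on the assumed 80%. The primary TOI comparison is unaffected. The change is worth making before recruitment, because reasons for early abandonment are hard to recover later.

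**What to change.** - Give the CSUQ and the three open questions also at the existing 12-week questionnaire contact (already used for FACT-L and HADS), and when a patient stops using the app or leaves the study. State what counts as having stopped using the app.
- Allow paper or telephone completion in the intervention arm. Both modes are already planned for controls.
- Say whether the end of the study means week 24 or each patient's own exit, and how the feedback session is held and recorded.
- Report ratings separately for week 12, end of study and exit; pooling each patient's last rating would mix time points. For each, give the number of responders out of all patients randomised to LuCApp, with bounds for non-responders as in Step 5.
- Show login and activity data for all patients randomised to LuCApp alongside the ratings.

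The cost is protocol wording, a few extra minutes for patients to complete a 12-item form, and some calls to those who stop. Patients who die before week 12 will still have no rating, so the bounds remain necessary.
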